and will only be available to research and clinical staff. Study data will be identified by participant code only, and no identifying information will ever be stored in association with participant data. Data will only be available to government or regulatory agencies as required by law. Prior to any assessment, participants will be informed of the limits of confidentiality regarding suicidal or homicidal intent, child or elder abuse, or inability to care for the self. All data will be stored on encrypted drives or a secure server within the Butler Hospital information technology system. Electronic data will be stored on password-protected computers. All electronic communications will be transmitted via secure, encrypted servers. No PHI will be included in any electronic communications. All paper records will be stored in a locked file cabinet within a locked office on Butler Hospital grounds. Butler Hospital has clear HIPAA regulations in place to ensure research compliance for both psychiatric and medical records. Additionally our mobile software service (ilumivu.com) is a HIPAA-compliant platform for the collection of EMA data and secure transmission of those data to a cloud-based central server with dedicated data backup. Study phones will be encrypted and password-protected and wiped clean of data before reuse. Text messages will only be sent from a phone dedicated for use in this research study, and will only be accessible to research staff. All text and email communications will be limited to scheduling research-related appointments or study-related reminders, and will not send any messages containing urgent information or protected health information.

D3. Data Safety Monitoring Plan

1. Data management and protection.

[name] will have responsibility for day-to-day monitoring of the quality of operations in all data collection. There are several sources of data. Research participants will complete questionnaires. Research assistants also code all data from research interviews. Only the participants' study identification number will appear on any of the final paper data collection instruments. Finally, audio recordings of interviews with participants will be uploaded and stored on a secure server in a digital format. A study ID will be used to identify the recordings. Otherwise, they are not connected with the primary study database in any way.

This study will use Care New England's instance of REDCap for the collection and storage of data. The study will not collect or store any actual data within REDCap until the project has been moved into REDCap's production environment. REDCap is a secure, web-based application developed by Vanderbilt University for building and managing surveys and databases. It is primarily designed to support online or offline data capture for research studies, quality improvement, and operations. REDCap provides easy data manipulation (with audit trails for reporting, monitoring and querying patient records), real-time data entry validation, and an automated export mechanism to common statistical packages. Care New England's instance of REDCap is hosted within the Care New England data center in Warwick, RI. This REDCap instance is role-based and is fully integrated with CNE's Active Directory structure. It enjoys 24/7/365 enterprise-level support and security inherit to CNE's HIPAA-compliant data center. Network transmissions (data entry, survey submission, and web browsing) to and from REDCap are protected via TLS 1.2 encryption. REDCap's data is stored on encrypted servers within CNE's data center. The REDCap Consortium is composed of thousands of active institutional partners in over one hundred countries who utilize and support REDCap. REDCap was developed specifically around HIPAA-Security guidelines, and more information about the consortium and system security can be found at <http://www.projectredcap.org/>.

All data collected by the research team are considered part of the subject's confidential record. Paper data forms collected from research participants will be kept in a locked file cabinet. All data will remain confidential. All data is stored on a secure research server, and backed up daily. Patient identifying information will be stored in a separate database and will be password protected in addition to being on a secure server.

2. Safety Plan and Adverse Event Identification and reporting

[name] will be responsible for overseeing the daily safety of all participants. There are several ways in which they will become aware of adverse events. First, research staff will ask patients about serious adverse events (as defined by Office of Human Research Protections (OHRP); e.g., inpatient hospitalization). Second, all study staff will be trained in the OHRP definitions of adverse events that are also unanticipated problems; serious adverse events; or unanticipated problems that are not adverse events. All study staff are required to report any event that might meet one of these criteria to one of the PIs immediately both verbally and in writing. Any report of a serious adverse event will result in one of the PIs contacting the participant to further assess the event.

Adverse Events Definitions

Adverse Event – any unfavorable and unintended sign, symptom or disease temporally associated with the use of a medical or behavioral treatment or intervention regardless of whether it is considered related to the treatment or intervention.

Expected Adverse Event – an event that may be reasonably anticipated to occur as a result of the study procedure and is described in the consent form.

Unexpected Adverse Event – any adverse event which is not described in the consent form and is unanticipated. An event that might have been anticipated but is more serious than expected or occurs more frequently than expected, would be considered an unexpected adverse event.

Serious Adverse Event - (21 CFR 312) include any untoward medical occurrence that at any dose results in death or the immediate risk of death, hospitalization or prolonging of an existing hospitalization, persistent or significant disability/incapacity or a congenital anomaly/birth defect (NIH guide-6/11/99).

Study Definitions

Specifically, we will consider the following events Serious Adverse Events (SAE):

- a. Death for any reason;
- b. A suicide attempt, defined as any action taken with intent to die, as stated by the patient or noted in the medical record;
- c. Inpatient psychiatric hospitalization

Additionally, we will consider the following events non-serious Adverse Event (AE):

- a. Evidence of coercion to participate;
- b. Participant distress resulting in stopping of the assessment or intervention;
- c. Access of confidential information by a non-authorized person.

Severity

Each adverse event will be graded in terms of severity:

- a. Non-severe adverse event
- b. Severe adverse event resulting in hospitalization or prolongation of existing hospitalization, a persistent or significant disability/incapacity.
- c. Life-threatening adverse event
- d. Fatal adverse event

Attribution

For each adverse event, one of the following attributions is assigned:

- Definite: Adverse event is clearly related to intervention
- Probably: Adverse event is likely related to intervention
- Possible: Adverse event may be related to intervention
- Unlikely: Adverse event is doubtfully related to intervention
- Unrelated: Adverse event is clearly not related to intervention

Suicidality. Because we will be recruiting individuals with psychiatric disorders, we may have some participants who disclose having suicide ideation or behavior. At the time that suicidality is identified by any study staff member for in-person assessments, they will contact a study clinician who will immediately evaluate that person. All study staff (e.g., research assistants) are trained in the Psychosocial Research protocol for managing suicidality. All clinical faculty in our research group, including [name] are experienced in management of suicidality and other clinical emergencies. [name], both licensed psychologists, will be available during regular business hours. After hours there is always a licensed mental health clinician (psychologist or psychiatrist) available on call by cell phone or pager in the Psychosocial Research Program.

When a clinician is asked to conduct an immediate evaluation, he or she will use our standard guidelines for conducting a suicide risk assessment. The clinician will determine whether it is necessary to take immediate action to prevent the participant from causing harm to him/herself. If needed, the study clinician may have a family member bring the person to Butler Hospital, send an ambulance, or transfer the participant to the Emergency Department at Memorial Hospital. If the participant is not in immediate danger of hurting him or herself, we will take the following actions. First, we will inform the patient about procedures for contacting emergency services should they find themselves at risk for self-harm. Second, with the patient's permission, we will contact their primary care physician or other clinician to inform them of the suicidality. We will urge the patient to make an appointment with that provider to discuss treatment options. Third, if the patient consents, we will speak with one of their family members to ensure that he/ she is aware of the seriousness of the patient's symptoms and the agreed-upon treatment plan. We will provide treatment referrals if the patient wishes. Regardless of outcome, suicide assessments are always documented in writing.

Mobile device data will be uploaded onto secure servers remotely. As real-time data review is not feasible or sustainable in typical clinical settings, mobile data will be reviewed weekly by research staff. This type of strategy is known as asynchronous communication (where there is a gap between communications compared with synchronous or "live" communication) and is often adopted in mobile health research. Patients will be informed that their responses will be reviewed periodically (not in real time), and that they may be contacted by study staff if safety risk is detected for the purposes of providing further assessment and assistance as necessary.

Adverse Event Reporting. Based on the sources of information detailed above as well as direct patient contact and/or consultation with the scientific team, [name] will determine if the event is: a) an adverse event that is also an unanticipated problem related to study procedures or intervention; b) a serious adverse event; or c) an unanticipated problem that is not an adverse event. Considering the nature of the study and sample, we expect serious adverse events to occur, including suicide attempts and rehospitalizations (e.g., due to relapse). However, given the nature of the study, it is unlikely that SAEs will be related to the study procedures. The other adverse events that are possible include: inadvertent disclosure of protected health information and coercion. If any of these adverse events occur, or any other unanticipated events that are identified, the following procedure will be activated:

The research staff member who observes or is notified of an adverse event will contact the MPIs or their designee immediately. The MPIs or their designee will complete a Butler Hospital IRB Adverse Event Form for each event that will include a level of severity and determine attribution (intervention-related or not). Reporting timeframes will vary by SAE type;

- 1) **expected and unrelated SAEs:** reviewed by the MPIs and reported to Butler IRB within 14 days ascertainment; provided to the DSMB in bi-annual data reports;
- 2) **unexpected or related SAEs:** to Butler IRB and DSMB within 10 days of ascertainment;
- 3) **all deaths:** to Butler IRB and DSMB within 5 days of ascertainment.

3. Data and Safety Monitoring Board (DSMB)

The DSMB will be constituted and will be responsible for monitoring the safety of participants and the quality of the data, as well as deciding on the appropriate termination of the study either when significant benefits or

risks have been uncovered or when it appears that the clinical trial cannot be concluded successfully. Members of the DSMB include [name]. (Chair; Professor, Boston University), [name]. (Associate Professor, Massachusetts General Hospital), and [name]. (Assistant Professor, Duke University). These DSMB members have experience serving on other DSMBs and conducting research on severe mental illness and mobile technologies.

Both MPIs and the DSMB Chair will develop the Data Safety Monitoring Plan. It will then be circulated to the rest of the DSMB for feedback and approval. The board members will review the initial DSMB protocol to ensure that it captures the information necessary to evaluate the safety and efficacy of the study. The DSMB will then receive DSM reports bi-annually. A DSM report will include concerns about significant safety and data monitoring issues such as recruitment, retention, and quality of data collected.

Operating procedures of the DSMB include monitoring the protocol to evaluate the safety of the participants as pre-specified in the DSMP of the protocol, monitoring efficacy of the intervention being tested, and evaluating performance of the trial, as well as study admission data and protocol compliance. The specific content of the reports to the DSM include information about AEs and/or SAEs, treatment retention, recruitment, reasons for dropout, and interim efficacy data.

Only reports that meet the criteria of being a death (within 5 calendar days) or unexpected and related to study procedures (within 10 calendar days) will be reported to the DSMB within the specified timeframe after learning of the event. Summary reports of all adverse events will be provided to DSMB in bi-annual reports. Finally, as part of the annual progress report (noncompeting continuation application) to NIH, we would provide summary information on all adverse events that have occurred during that year.

As they deem necessary, the members of the DSMB will evaluate whether the presence of early unanticipated therapeutic results, side effects or adverse consequences are significant enough to warrant amendment, suspension, or early termination of the study and will independently make recommendations to the PIs to continue, to amend or to terminate the trial. Recommendations related to the study will be made in a written DSMB Report by the Board's Chairperson to the Principal Investigator and this DSMB Report, along with the DSMB meeting minutes, will be sent to the NIH Project Officer for the study.

E. Potential Benefits

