Communication with outpatient providers. At baseline, an initial discharge report will be sent by the study clinician to patients' outpatient providers (after obtained releases of information from the patient) based on assessment results. Additionally, to improve quality of care and timely communication between providers, periodic reports (e.g., bi-weekly the first month and monthly thereafter containing information on symptoms, safety, and adherence) will be sent to patients' outpatient clinicians throughout the study to improve care coordination. These reports will be generated using data collected via the app.

Assessment Procedures (see Table 1)

Participants will complete baseline measures, as well as diagnostic interviews at intake prior to hospital discharge (~1.5 hrs). Patients will return to our research office to complete traditional assessments at 1, 2, and 4 months to assess longer-term effects (~1 hr each).

MACS app assessments. MACS assessment items are adapted from traditional measures and those used in other mobile studies in psychosis: a) affect³⁸, b) psychosis¹⁵, c) social support¹⁰², d) life satisfaction³⁹, e) functioning⁴⁰, f) treatment adherence⁴¹, g) substance use⁴², h) safety⁴⁴.

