Clinical Outcomes and Other Measures. In addition to target mechanisms, we will assess clinical outcomes including: a) symptom severity (primary outcome), b) functioning, and c) re-hospitalization rates. a) We will use the BPRS⁵⁶ a well-established interview measure of overall psychiatric symptom severity, including positive/negative psychotic symptoms, as well as mood symptoms and suicidality; b) the WHODAS-2^{39,40}, which is a brief self-report measure of functional impairment; and c) rehospitalizations obtained from the THI-4⁵⁰ as described above (and cross-checked with patients' medical records). In addition, the THI-4 will also be used to quantify overall treatment utilization, including the type and amount of mental health treatment received over follow-up (medications, psychosocial, hospitalizations, pharmacotherapy visits, ER visits, crisis calls, support groups). We also will administer the AUDIT/DUDIT, which measure alcohol/drug use and severity^{42,58,64}. The MMSE⁶³ will be used to assess cognitive functioning at baseline in order to describe patients' baseline characteristics and to examine this variable as a potential predictor of treatment response in our analyses. The AMBAS⁶⁵ is a brief self-report measure of medication beliefs. Acceptability/satisfaction with the mobile apps will be assessed using an adapted version of the CSQ-8⁵⁷ at the end of the study. Finally, participants will complete an end-of-treatment interview in which they will be asked what they liked and did not like about the app and study participation.

C4. Data Analysis

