Midway (n=10) and at the end of the open trial (n=20), we will examine development outcomes (e.g., mobile session completion rates, recruitment/retention, satisfaction). We will use descriptive statistics to summarize variables. If development targets are not met, the research team will investigate and discuss the issue, and depending on the perceived reasons for the discrepancy, may modify research procedures to address the issue. For example, if mobile completion rates are low, we will modify instructions or change procedures (e.g., frequency, length, timing) to increase rates. Further, we will calculate effect sizes to characterize changes over the follow-up in our target mechanisms of medication adherence (MEMS), appointment adherence (THI-4) and active self-coping (MACS-II). We will report clinical significance statistics (number-needed-to-treat/NNT, area under the curve/AUC) to further examine effects. We also will examine effect size changes in primary (overall symptom severity=BPRS) and secondary outcomes (functioning=WHODAS-2; rehospitalization rates=THI-4).

D. Material Inducements

We will compensate patients for completion of in-person assessments (\$30 each at the baseline, 1, 2, and 4 month follow-ups, with an additional \$20 for returning the electronic pill caps or a borrowed study phone, if applicable, for up to \$140 total), but not mobile device use, to reflect real world practice.

E. Training of Research Personnel

The research assistants (RAs) will be directly supervised by [name]. All RAs in the psychosocial treatment program undergo extensive training in screening medical records (including the appropriate permissions to access electronic medical records), approaching patients on the units, obtaining consent to participate, collecting and entering data, and maintaining confidentiality. All RAs have received training in the informed consent process and their ethical responsibilities when conducting research. Additionally, all RAs will receive specific training in the assessment instruments to be administered. [name] also will train and supervise the master's level clinician who will meet with patients for the initial app session before discharge and send brief reports during the study to patients' community clinicians based on assessment data collected.

3) Human Subjects

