A. Subject Population (include number; gender; age; diagnosis; inpatient vs. outpatient; physical health; inclusion/exclusion criteria; rationale for use of special groups)

Participants in this study will consist of 20 patients diagnosed with schizophrenia-spectrum disorders who have

Date most recently revised (02/15/19)

Protocol Version 1.2

been hospitalized for acute psychiatric reasons at Butler Hospital.

Inclusion criteria are: (1) currently hospitalized; (2) DSM-5 criteria for schizophrenia or schizoaffective based on the Structured Clinical Interview for DSM-5⁵⁵ (SCID-5); (3) 18 years or older; (4) prescribed oral antipsychotic medication upon discharge; and (5) ability to speak and read English (materials written at a 5th grade reading level).

Exclusion criteria are: (1) alcohol/drug use disorders at moderate or severe level based on SCID (mild substance use disorders will be permitted); (2) planned discharge to supervised living setting or participation in formal outpatient adherence programs (e.g., medication packaging); or (3) pregnancy or other medical condition (e.g., dementia as indicated by patients' medical charts) contraindicating use of antipsychotic medications.

B. Recruitment and Consent Procedures

If the patient appears appropriate based on the routine electronic chart review of hospital admissions, the study will be explained to the patient's treating physician. If the physician agrees it is clinically appropriate, a member of the research team will then approach the patient. All participants will be asked to provide releases of information for their community treatment providers so that the investigators can obtain records to corroborate patient self-report of treatment utilization and send brief reports to clinicians at follow-up. We also will collect the names and numbers of additional contact persons and collect permission to contact them in the event that we are not able to reach the patient during the study. After obtaining permission for this purpose, we will contact participants via text and/or email to schedule follow-up contacts and check in with them periodically to prompt their use of the app.

C. Potential Risks

Potential risks of study participation include: coercion, clinical deterioration/suicidality, loss of confidentiality/privacy, and adverse events (see details below).

D. Protection of the Subject

D1. Measures to Minimize Potential Risks

Coercion

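### C4 plans a number-needed-to-treat, but this single-arm trial has no comparator, reference response rate or responder definition to compute it from; the paired AUC is undefined

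*Combined protocol and SAP*

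**What the plan says.** C4 first plans descriptive statistics for development outcomes (session completion, recruitment and retention, satisfaction), reviewed at n=10 and n=20. It says procedures may be modified if development targets are missed. It then turns to outcomes. For the target mechanisms it will "calculate effect sizes to characterize changes over the follow-up in our target mechanisms of medication adherence (MEMS"), together with appointment adherence (THI-4) and active self-coping (MACS-II). The next sentence reads: "We will report clinical significance statistics (number-needed-to-treat/NNT, area under the curve/AUC) to further examine effects". The section closes: "We also will examine effect size changes in primary (overall symptom severity=BPRS) and secondary outcomes (functioning=WHODAS-2; rehospitalization rates=THI-4").

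NNT and AUC are named only in that one sentence. No formula, outcome, contrast or time point is attached to either.

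The opening aims statement, C1 and C2 describe one open-trial group of 20, all given the app. C2 gives the trial's purpose as acceptability and feasibility, while the opening statement also lists potential effectiveness among the things the project examines. A controlled comparison is mentioned only as a possible later RCT (C3, MACS Protocol).

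**The concern.** An NNT answers how many patients must be treated for one more to benefit than would have done otherwise. The second half of that question needs a response rate without the treatment, and this trial neither observes one nor names one. It also needs a rule for who counts as a responder. Section C3 (Clinical Outcomes and Other Measures) plans to take baseline MMSE and "examine this variable as a potential predictor of treatment response in our analyses", but no threshold for response is given there or elsewhere.

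C4 says these statistics will be reported, calls them measures of clinical significance, and gives their purpose as examining effects. A reader of the eventual report would take a published NNT as the benefit of MACS. The risk is one of interpretation: a number that looks like a treatment effect, from a design that cannot supply one.

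**Working it through.** The documents give no NNT, AUC, response rate or effect size, so there is no planned figure to reproduce. The sample size of 20 is theirs (C1). **Every response rate, d and r below is assumed for illustration.** The results show dependence on unstated inputs, not the size or direction of any bias.

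**1. NNT needs a reference rate.** NNT = 1/(p_MACS - p_ref). Assume 10 of 20 respond, so p_MACS = 0.50, with exact (Clopper-Pearson) 95% CI 27.2% to 72.8%. The reference rate is treated as fixed, and the interval for the difference is the interval for p_MACS minus p_ref.

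| Assumed p_ref | Difference | NNT | 95% CI for difference (points) |
|---|---|---|---|
| 0% | 0.50 | 2.0 | 27.2 to 72.8 |
| 20% | 0.30 | 3.3 | 7.2 to 52.8 |
| 40% | 0.10 | 10 | -12.8 to 32.8 |
| 50% | 0 | infinite | -22.8 to 22.8 |
| 60% | -0.10 | -10 | -32.8 to 12.8 |

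The same data give strong benefit, nothing or harm according to a number the plan does not contain. At 40% and above the interval for the difference includes zero, so the NNT interval passes through infinity. Even with the reference set to 0%, sampling error alone spreads the NNT from 1/0.272 = 3.7 to 1/0.728 = 1.4.

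**2. A before-after conversion depends on an unstated definition.** Assume a standardized change of d = 0.5.

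- Time points treated as independent groups: AUC = Φ(d/√2) = 0.638, and NNT = 1/(2·AUC - 1) = 3.62.
- Paired, as a within-patient probability of improvement: Φ(d/√(2(1 - r))) = 0.664, 0.691 or 0.741 for r = 0.3, 0.5 or 0.7. The same conversion gives NNT = 3.05, 2.61 or 2.08.

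One assumed change gives NNTs from 2.1 to 3.6 according to choices C4 does not make.

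**3. A before-after conversion is also confounded.** It uses each patient's pre-discharge state as the untreated reference. Section 3A requires an acute admission at entry ("Inclusion criteria are: (1) currently hospitalized"), and C3 records "the type and amount of mental health treatment received over follow-up". The course after that admission and the community treatment would both be counted as MACS. Suppose the app did nothing and these alone moved scores by d = -0.5 to 0.8:

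- independent-groups AUC: Φ(-0.5/√2) = 0.36 to Φ(0.8/√2) = 0.71;
- paired, r = 0.5, where d/√(2(1 - r)) = d: Φ(-0.5) = 0.31 to Φ(0.8) = 0.79.

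The true value for an inert app is 0.50 on both scales. The direction is open: the Background describes coping and adherence as being at risk after discharge, while symptoms are first rated during an acute admission.

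**4. Which outcomes allow a before-after reading.** Table 1 schedules MEMS at months 1, 2 and 4 with no baseline, so it supports change across follow-up but not change from before the app. THI-4 has a baseline, with no look-back period stated. Any before-after contrast in hospitalization would be distorted because every patient is selected for a current admission.

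**The case against.** The best reply is that NNT and AUC are descriptive conversions of the within-group effect sizes in the sentence just before. That is a natural reading, but C4 does not say so. It would change the fault from an inestimable quantity to an undefined and misleadingly labelled one; the confounding in step 3 would remain.

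Several stronger readings are tempting, and the documents do not support them:

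- *AUC is impossible in one arm.* It is not. A within-patient probability of improvement is estimable, and so is an ROC AUC for a baseline predictor such as MMSE once response is defined. What stands is that C4 does not say which is meant.
- *The planned MEMS effect size cannot be computed.* C4 asks for change over the follow-up, and months 1, 2 and 4 supply it. Only a contrast with a pre-app value is missing.
- *Provider reports and staff contact are further confounders.* C3 says that "periodic reports (e.g., bi-weekly the first month and monthly thereafter containing information on symptoms, safety, and adherence) will be sent to" outpatient clinicians, and section 3B says staff will "check in with them periodically to prompt their use of the app". The reports are built from app data and the prompts serve app use, so both are arguably part of the delivered package. The argument does not need them.
- *The figures would be inflated.* The direction is unknown.
- *The decision to proceed to an RCT turns on NNT.* C3 makes a later RCT conditional on the project's success but does not define success by NNT or AUC.
- *A comparison group exists.* The wording on app users under Mobile Device Use might hint at one, but none is described.

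The objection on importance also stands: these are supplementary statistics in a feasibility trial, and C4's action rule rests on development targets.

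**Conclusion.** Wrong as written; low severity. C4 commits to an NNT that a single group of 20 cannot yield as a treatment effect, because no comparator, reference rate or responder rule is given. That conclusion rests on the design and on what the plan leaves out, not on the assumed rates above. Those rates show only that the reported value would be set by an unstated input. For AUC the conclusion is narrower: it is undefined, and reading it as an effect of MACS would meet the same confounding.

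A reader might infer that the trial's main purpose is compromised. It is not: the feasibility and acceptability aims and the action rule in C4 are unaffected.

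**What to change.** Amend C4 as follows.

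- **NNT:** delete it, and reserve it for a controlled trial.
- **AUC:** delete it, or define it as the within-patient probability of improvement from baseline to month 4. If an ROC AUC for a predictor was meant, say so and define response.
- **Effect sizes:** keep the planned within-person effect sizes, each with a 95% CI and the number of participants contributing, labelled *change during MACS use, not an effect of MACS*.
- **MEMS:** report levels at months 1, 2 and 4 and change across follow-up.
- **Rehospitalization:** report the proportion by month 4 with an exact 95% CI. For example, an assumed 6 of 20 is 30%, with 95% CI 12% to 54%.

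The cost is a few sentences. No new visit or measure is needed, since all the data are already scheduled in Table 1. The report loses a single clinical-significance number to quote, and its intervals will be wide: an assumed standardized within-person change of 0.5 has a 95% CI of 0.03 to 0.96 at n=20 (noncentral t).
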